## **2 Study objectives**

### **2.1 Primary objective(s)**

- To demonstrate that serelaxin is superior to placebo in improving the clinical composite of “treatment success,” “treatment failure” and “unchanged”
  - Treatment success is defined as moderate or marked improvement in patient reported dyspnea by Likert scale AND  $\geq 2$  points improvement for at least 2 out of 4 physician assessed signs and symptoms including orthopnea, rales, edema and JVP and none of them deteriorating ( $\geq 0$  point improvement) at Day 2.  
Refer to the Efficacy assessment 1 [Section 6.4.1](#) and the physician assessment of signs and symptoms [Section 15 Appendix 3](#).
  - Treatment failure is defined as in-hospital worsening of heart failure or re-hospitalization due to HF or RF or death through Day 5.

- All remaining patients are classified as having unchanged treatment status if they meet neither the criteria for treatment success at Day 2 nor the criteria for treatment failure through Day 5.

Worsening heart failure (WHF) is defined as in-hospital worsening signs and/or symptoms of heart failure that require an intensification of intravenous therapy for heart failure or mechanical ventilator, renal or circulatory support. Such treatment can include the institution or up-titration of IV furosemide, IV nitrates or any other IV medication for heart failure, or institution of mechanical support such as mechanical ventilation, ultrafiltration, hemodialysis, intra-aortic balloon pump or ventricular assist device.

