### 4.1 Inclusion criteria

Subjects must fulfill all of the following criteria at screening to be eligible for the study. The screening period is defined as that interval that begins at the time the informed consent is signed and ends with the qualification of the subject for entry into the study (i.e. when subject is determined to meet all eligibility criteria):

1. Written informed consent must be obtained before any study-specific assessment is performed\*
2. Male or female  $\geq 18$  years of age, with body weight  $\geq 30$ kg and  $\leq 160$  kg
3. Hospitalized for AHF; AHF is defined as including all of the following measured at any time between presentation (including the emergency department and outpatient clinic) and the end of screening:
  - Persistent dyspnea at rest or with minimal exertion at screening and at the time of randomization
  - Pulmonary congestion on chest radiograph
  - BNP  $\geq 500$  pg/mL or NT-proBNP  $\geq 2,000$  pg/mL
4. Systolic BP  $\geq 125$  mmHg at the start and at the end of screening

5. Able to be randomized within 16 hours from presentation to the hospital, including the emergency department and outpatient clinic.
6. Received intravenous furosemide of at least 40 mg total (or equivalent) at any time between presentation (this includes outpatient clinic, ambulance, or hospital including emergency department) and the start of screening for the study for the treatment of the current acute HF episode
7. Impaired renal function defined as an eGFR between presentation and randomization of  $\geq 25$  and  $\leq 75\text{mL/min}/1.73\text{m}^2$ , calculated using the sMDRD formula (or modified sMDRD formula according to specific ethnic groups and local practice guidelines). ([Levey et al 2006](#); [Ma et al 2006](#); [Matsuo et al 2009](#); [Townamchai et al 2013](#)).

\* *Patient assessments of AHF that are per current local institutional/hospital standard protocol or part of routine clinical care that are performed within 16 hours from presentation are allowed before signing informed consent, and can be used to support patient screening.*

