### **5.5.7      Concomitant treatment**

To be eligible for the study, all patients must have received IV furosemide of at least 40 mg (or equivalent) at any time between presentation to emergency services (this includes outpatient clinic, ambulance, or hospital including emergency department) and screening for the study.

Patients will not be enrolled in the study if concomitant therapy for AHF includes current (within 2 hours prior to randomization) or planned (through the completion of study drug infusion) treatment with any cardiovascular IV therapies, including vasodilators (including nesiritide and carperitide), positive inotropic agents and vasopressors, or mechanical support (intra-aortic balloon pump, endotracheal intubation, mechanical ventilation, or any ventricular assist device), with the exception of IV furosemide (or equivalent), or IV nitrates at a dose of  $\leq 0.1$  mg/kg/hr if the patient has a systolic BP  $> 150$  mmHg at screening. Use of IV furosemide (40 mg or equivalent) is an inclusion criterion; further doses of IV furosemide can be administered at any time after enrollment. Furosemide may not be administered using the same infusion bag or infusion line as study drug.

Major cardiovascular and non-cardiovascular classes of medication taken by a subject approximately 30 days prior to study drug initiation and on a daily basis while hospitalized through Day 5, at Discharge, Days 14 and 30 (telephone visit) and at Days 60, 120 and 180 will be recorded. Only those medications currently being taken or those were taken within 24 hours prior to the visit will be collected. These include but are not limited to: loop diuretics, other diuretics, ACE inhibitors, angiotensin receptor antagonists, beta-blocker, hydralazine, nitrates, calcium channel blockers, digoxin, non-steroidal anti-inflammatory agents, COX-2 inhibitors, aminoglycoside antibiotics, inotropes, vasodilators and others (e.g. insulin, oral anti-diabetics, statins, anticoagulants etc.).

The investigator may prescribe any additional medications during the study as dictated by the patients' condition. Administration of standard treatment should in no instance be delayed or withheld due to patient's participation in the study. Standard treatment includes, but is not limited to, administration of the major classes of medications, as described above, as well as administration of oxygen, analgesics, anxiolytics and sedatives, as needed.

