##### **6.4.4.2 Worsening of heart failure**

Worsening heart failure (WHF) is defined as in-hospital worsening signs and/or symptoms of heart failure that require an intensification of intravenous therapy for heart failure or mechanical ventilatory, renal or circulatory support. Such treatment can include the institution or up-titration of IV furosemide, IV nitrates or any other IV medication for heart failure, or institution of mechanical support such as mechanical ventilation, ultrafiltration, hemodialysis, intra-aortic balloon pump or ventricular assist device.

The investigator will evaluate the patient for early in-hospital worsening heart failure events at 6, 12, 24 and 48 hours from the start of study drug infusion, and then daily while hospitalized through Day 5 or at discharge whichever is earlier (Refer to [Table 6-1](#)). These evaluations should be done at the same time of day, each day, in the same position, and hospital/clinic setting, preferably by the same assessor. To ensure consistency, if the same assessor cannot perform the daily assessments, the second assessor should evaluate the patient

together with the first assessor at least once prior to performing the assessments independently. Only physicians who have completed the training of the protocol based standardized measurements can obtain the physician assessed signs and symptoms for this study.

Index in-hospital worsening heart failure events will be adjudicated by the CEC. The procedures of the adjudication will be described in the *CEC Charter*.

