2.2.2 Secondary efficacy variables and analyses

There are three secondary variables:

- WHF through Day 5
- CV death through Day 180
- All-cause death through Day 180

All of these secondary variables are time-to-event variables. The hypothesis will be tested based on the FAS at a significance level of 0.025 (one-sided).

The three secondary variables will be tested using hierarchical testing procedure in controlling overall α of 0.05 (Bretz et al 2009). If primary endpoint is significant, WHF will be tested first at α of 0.05. If WHF is significant at the same α level then will proceed to test CV death and only if CV death is significant then will test all-cause death at α of 0.05.

WHF through Day 5

Time to WHF through Day 5 will be analyzed using Gehan's generalized Wilcoxon test. Subjects died in the 5-day period will be considered as having WHF event. Event date and time will be used at calculating the time to event for better precision, and convert it back to days.

Time-to-event (days) = (first event date/time – baseline date/time),

For those subjects without events, the censoring date will be the earlier of

- Hour 120 (5 days)
- The last date at which the vital status was known, including last visit or contact

Kaplan-Meier curves will be presented graphically by treatment group and Kaplan-Meier estimates for selected time points with 95% confidence intervals will be tabulated.

In addition, analyses will be performed using a modified definition of WHF, e.g. subjects with (1) worsening signs AND symptoms or (2) IV intervention and/or mechanical support. Another sensitivity analyses that exclude subjects whose only symptom is abdominal bloating/discomfort or fatigue/decreased exercise tolerance will also be provided.

CV death through Day 180

CV death will be analyzed with a log-rank test. The time-to-event will be calculated days by subtracting the randomization date from the event date. Number and percentage of subjects who died from cardiovascular reasons based on the number of subjects in the population as denominator will be provided by treatment group. The hazard ratio (relative risk) and its associated two-sided 95% confidence interval will be estimated based on a Cox proportional hazards model with treatment assignment as a factor.

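### A WHF sensitivity analysis in SAP 2.2.2 removes randomized patients because of how their event presented; it should recode the event and keep the patient

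*SAP*

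**What the plan says.** Protocol 6.4.4.2 (also 2.1 and 6.4.1) defines WHF as "in-hospital worsening signs and/or symptoms of heart failure that require an intensification of intravenous therapy", or mechanical ventilatory, renal or circulatory support. Two things are therefore needed: worsening, and intensified treatment because of it.

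SAP 2.2.2 tests time to WHF through Day 5 in the FAS with Gehan's generalized Wilcoxon test. Deaths within the five days count as events, and patients without an event are censored at Hour 120 at the latest. The same section then adds two kinds of robustness analysis:

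- a "modified definition of WHF, e.g. subjects with (1) worsening signs AND symptoms or (2) IV intervention and/or mechanical support";
- a further analysis, worded as "Another sensitivity analyses that exclude subjects whose only symptom is abdominal bloating/discomfort or fatigue/decreased exercise tolerance".

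For neither does it say how the affected patients are scored or censored. SAP Table 2-5 lists no WHF sensitivity analysis, so this paragraph is the only specification in the supplied text.

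**The concern.** The exclusion rule cannot refer to a baseline trait. Protocol 4.1, criterion 3, requires persistent dyspnea at screening and again at randomization, so no eligible patient has bloating or fatigue as the only symptom at entry. The rule must describe the symptom recorded for the WHF event after randomization. Three things follow if it is applied as written:

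- Randomized patients leave the FAS because of their outcome, and the two arms no longer lose comparable patients.
- A patient removed for a fatigue-only event who then has a clear WHF or dies before Hour 120 disappears together with that later event.
- The rule speaks of symptoms and is silent on signs. Fatigue with worsening rales or edema would be removed too, although it meets the base definition when treatment is intensified.

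The analysis exists to show whether the WHF result depends on soft events. It should not be biased in exactly the case where it does.

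The modified definition has a separate wording gap. Item (1) does not mention intensified treatment. Item (2) mentions neither worsening nor intensification.

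**Working it through.** The documents give no figure for either analysis and no share of soft events, so the shares below are assumptions shown as ranges.

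**Inputs**
- 760 patients per arm: 1,520 randomized 1:1 (Protocol 9.7, SAP 2.7).
- Event proportions 11.9% placebo and 6.4% serelaxin (Protocol 6.4.3). These are RELAX-AHF treatment-failure rates, which include death and re-hospitalization, and serve only as a proxy for WHF. Their ratio is 6.4/11.9 = 0.538. The protocol quotes a 45% relative reduction; the printed percentages give 46%, which makes no difference here.
- Soft share *f* of events (bloating or fatigue only): assumed 10% to 50%.
- No later qualifying event in the affected patients, so the tables show only the effect of the changed denominator.

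**Step 1: soft events proportional in both arms.** Keeping the patients as non-events gives *p*(1 − *f*) in each arm, so the risk ratio (RR) stays at 0.538. Dropping them gives *p*(1 − *f*)/(1 − *pf*). At *f* = 20%:
- removed: 0.119 × 760 × 0.2 = 18.1 placebo and 0.064 × 760 × 0.2 = 9.7 serelaxin;
- recoded: 9.52% v 5.12%, RR 0.538;
- dropped: 0.0952/0.9762 = 9.75% v 0.0512/0.9872 = 5.19%, RR 0.532.

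| Soft share | Removed, placebo / serelaxin | RR recoded | RR dropped |
|---|---|---|---|
| 10% | 9.0 / 4.9 | 0.538 | 0.535 |
| 20% | 18.1 / 9.7 | 0.538 | 0.532 |
| 30% | 27.1 / 14.6 | 0.538 | 0.529 |
| 50% | 45.2 / 24.3 | 0.538 | 0.523 |

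**Step 2: whole difference in soft events.** Let the remaining hard events occur in the same proportion *h* in both arms. The soft proportions are then 11.9% − *h* and 6.4% − *h*. Recoding gives *h* v *h*, RR 1.00. Dropping gives *h*/(1 − soft) in each arm, so RR = (1 − soft placebo)/(1 − soft serelaxin). At *h* = 3.0% this is 0.911/0.966 = 0.943.

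The one-sided chance of a nominally favourable result is Φ[(difference − 1.96 SE0)/SE1], with the pooled (SE0) and unpooled (SE1) binomial standard errors at 760 per arm. At *h* = 3.0% the difference is 0.00187 and both standard errors are about 0.0090, giving Φ(−1.75) = 4.0%.

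| *h* | Soft, placebo / serelaxin | Rates after dropping | RR | Chance (nominal 2.5%) |
|---|---|---|---|---|
| 3.0% | 8.9% / 3.4% | 3.29% v 3.11% | 0.943 | 4.0% |
| 5.0% | 6.9% / 1.4% | 5.37% v 5.07% | 0.944 | 4.5% |
| 6.4% | 5.5% / 0% | 6.77% v 6.40% | 0.945 | 4.8% |

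This is a binary approximation to the time-to-event test, with 760 per arm kept in the standard errors.

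**Step 3: modified definition, literal reading only.** If a share *q* of patients in both arms has post-baseline IV treatment unrelated to WHF and it counts as an event, the rates become *q* + (1 − *q*)*p*. With *q* assumed at 30%, this is 38.3% v 34.5%, and power falls from about 96% to 34%. With *q* at 95% it is 95.6% v 95.3%, and power is about 4%. The documents give no value for *q*.

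**The case against.** **On the exclusion rule.** The sentence does not say that patients leave the FAS; it could be loose wording for not counting their events. The shift under proportional soft events is negligible. The 4% to 5% figure needs the whole treatment effect to lie in soft events, and it concerns an analysis to which no alpha is assigned. SAP 2.2.3 also prespecifies WHF by symptoms only, signs only and both, and Protocol 8.5 has index in-hospital WHF adjudicated by the Clinical Events Committee. All of this limits the consequence. It does not repair the rule: the printed word is subjects, not events, and neither the signs/symptoms endpoint nor adjudication says how a bloating-only or fatigue-only patient is handled here.

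**On the modified definition.** A reader might infer that it makes nearly every patient an event, because all enter having received IV furosemide and "further doses of IV furosemide can be administered at any time after enrollment". The documents do not support that reading:

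- The items modify an existing definition and are introduced by e.g., so they can be shorthand that keeps worsening and intensification. They may also be two alternative definitions.
- The entry criterion is "Received intravenous furosemide of at least 40 mg total (or equivalent) at any time between presentation" and the start of screening. Event time runs from baseline, so that dose cannot be an event.
- Permission for further doses does not say how often they are given.

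What stands is that the definition is incomplete, not that it certainly miscounts. If the shorthand reading is meant, item (2) largely repeats the base definition and tests little that is new.

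A reader might also infer that the primary composite is at risk. SAP 2.2.2 attaches these analyses to the WHF secondary only, and Table 2-5 lists different sensitivity analyses for the primary.

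**Conclusion.** The exclusion rule is a real, minor defect. As worded, it selects on a post-randomization outcome and can lose later WHF events, deaths and sign-based WHF. With soft events proportional, the denominator effect moves the risk ratio from 0.538 to between 0.523 and 0.535 for assumed soft shares of 50% down to 10%. If the whole difference is in soft events, it gives 0.94 to 0.95 where the answer should be 1.00, with a one-sided false-favourable chance of about 4% to 5% instead of 2.5%. These sizes rest on failure rates standing in for WHF, on assumed soft shares and on a binary approximation. The loss of later events and of sign-based WHF cannot be sized from the documents.

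The modified definition is a secondary wording point: on a literal reading, routine post-baseline IV furosemide could count as WHF, at a frequency that the documents do not give. No decision rule changes, so this is worth correcting but not critical.

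**What to change.** In SAP 2.2.2, before unblinding:

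1. Replace the exclusion with recoding. Keep every FAS patient. Do not count a WHF event whose only symptom is abdominal bloating/discomfort or fatigue/decreased exercise tolerance and in which no sign worsened. Continue follow-up to the first later qualifying WHF, death or censoring under the main analysis rules.
2. State that both modified definitions are subsets of WHF events that already meet Protocol 6.4.4.2, each written out in full and analysed separately, and drop the open-ended e.g.

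The cost is a few lines of SAP text and minor reprogramming. The planned analyses already presuppose that symptoms and signs are recorded for each WHF event. One thing to confirm first is that the database holds WHF events after a patient's first one, since item 1 needs them.

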Data analysis	
The primary efficacy variable will be the trichotomous clinical composite endpoint based on (i) treatment 'success' of congestion improvement of dyspnea in Likert (moderately and markedly improvement) AND at least 2 points improvement for at least 2 out of 4 signs and symptoms variables at Day 2, (ii) treatment 'failure' of in-hospital worsening heart failure, death or re-hospitalization due to HF or RF through Day 5 and (iii) neither as 'no change'.
 
The primary analysis will be the comparison of two trinomial distributions of trichotomous clinical composite endpoint between placebo and serelaxin groups.
 
The primary statistical hypothesis is:
 
<math>H_0: \theta \geq 1</math> vs <math>H_a: \theta < 1</math>
 
Where <math>\theta</math> is the common value of two odds ratios of clinical composite endpoint ('failure' versus combined 'no change' and 'success' or combined 'failure' and 'no change' versus 'success') between placebo and serelaxin. <math>H_0</math> is the null hypothesis and <math>H_a</math> is the alternative hypothesis (Whitehead 1993). The hypothesis will be tested based on the FAS with an ordered logistic-regression (proportional odds) model that includes treatment and country as factors (McCullagh, 1980). Given the classification of (-1 denoting 'failure', 0 for 'no change' and 1 for 'success', an odds ratio of less than 1 would favor serelaxin. The odds ratio and 95% confidence interval for the treatment effect will be calculated and presented. There are three secondary variables:
 

• WHF through Day 5

• CV death through Day 180

• All-cause death through Day 180.

 
All of these secondary variables are time-to-event variables. The hypothesis will be tested based on the FAS at a significance level of 0.025 (one-sided).
 
The three secondary variables will be tested using hierarchical testing procedure in controlling overall <math>\alpha</math> of 0.05 (Bretz, et al 2009). If primary endpoint is significant, WHF will be tested first at <math>\alpha</math> of 0.05. If WHF is significant at the same <math>\alpha</math> level then will proceed to test CV death and only

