### **9.5 Analysis of secondary variables**

#### **9.5.1 Efficacy variables**

There are three secondary variables:

- WHF through Day 5
- CV death through Day 180
- All-cause death through Day 180.

All of these secondary variables are time-to-event variables. The hypothesis will be tested based on the FAS at a significance level of 0.025 (one-sided).

The three secondary variables will be tested using hierarchical testing procedure in controlling overall  $\alpha$  of 0.05 (Bretz, et al 2009). If primary endpoint is significant, WHF will be tested first at  $\alpha$  of 0.05. If WHF is significant at the same  $\alpha$  level then will proceed to test CV death and only if CV death is significant then will test all-cause death at  $\alpha$  of 0.05.

Time to WHF through Day 5 will be analyzed using Gehan's generalized Wilcoxon test. Patients died in the 5-day period will be considered as having WHF event. Patients without an event will be censored at the earlier of the last contact date or 120 hours after randomization. Kaplan-Meier curves will be presented graphically by treatment group and Kaplan-Meier estimates for selected time points with 95% confidence intervals will be tabulated.

For CV death and all-cause death will be analyzed with a log-rank test. Number and percentage of patients who died from cardiovascular reasons based on the number of patients in the population as denominator will be provided by treatment group. The hazard

ratio (relative risk) and its associated two-sided 95% confidence interval will be estimated based on a Cox proportional hazards model with treatment assignment as a factor.

In addition, for CV death and all-cause death, the Kaplan-Meier estimates of the survival functions for each treatment group will be plotted. The Kaplan-Meier estimates of the cumulative event rate will also be presented in tables by treatment group for each day and also by time interval.

For CV death, a patient without an event will be censored at the earlier of:

- Date of death for non-CV related causes
- The last date at which the vital status was known
- Day 180

For all-cause death, a patient without an event will be censored at the last date at which the vital status was known or at Day 180.

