2.1.6 Background and demographic characteristics

Subject demographics (age, sex, ethnicity, race, weight, height and BMI) and baseline characteristics will be summarized for the FAS populations. Screening BNP, NT pro-BNP and estimated eGFR, laboratory values as reported by the investigator will be summarized with standard descriptive statistics. The number and percentage of subjects who were hospitalized for heart failure in the past year and subjects on IV nitrates at the time of randomization will both be presented.

For baseline comparability, treatment groups will be compared using the chi-squared test for categorical variables and using t-test for continuous variables. The p-values will be provided for descriptive purpose and will not be considered to define any formal basis for determining factors to be included in statistical models. If an imbalance of treatment groups with respect to some variables does occur, supplemental analyses with addition of these variables in model may be performed to assess the potential impact on efficacy as appropriate.

In addition, violations of inclusion and exclusion criteria and other protocol deviations will be listed. Major protocol deviations resulting in subject exclusion from any analysis ([Table 2-1](#)) will be summarized by treatment group for RAN population.

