2.2 Efficacy evaluation

The Full Analysis Set (FAS) is the primary analysis population for efficacy analyses, following the intention-to-treat principle. Per-protocol (PPS) population will be used in the supportive analysis for primary and key secondary efficacy parameters (Table 2-5).

Table 2-5 List of efficacy endpoints and analyses

Endpoint	Analysis set	Analysis method
Primary efficacy endpoint ($\alpha=0.025$, 1-sided)		
1 Trichotomous composite (success, failure, no change)	FAS/PPS	Ordered logistic-regression (proportional odds) model that includes treatment and [REDACTED] as factors (primary analysis is on FAS)
	FAS	Ordered logistic-regression model including treatment only (sensitivity analysis 1)
	FAS	van Elteren extension of the Wilcoxon test stratified by [REDACTED] (sensitivity analysis 2)
Secondary efficacy endpoints (if primary endpoint is significant, then test in the order listed below at $\alpha=0.05$ each)		
1 Time (hours) to WHF through Day 5	FAS/PPS	Gehan's generalized Wilcoxon test
2 Time (days) to CV death through Day 180	FAS/PPS	Kaplan-Meier estimates and log-rank test
3 Time (days) to all-cause death through Day 180.	FAS	Kaplan-Meier estimates and log-rank test
Other efficacy endpoints (at $\alpha=0.05$, no multiplicity adjustment)		
1 Time (hours) to moderate or marked improvements in dyspnea by Likert scale through Day 5	FAS	Wilcoxon rank-sum test
2 Dyspnea by VAS-AUC changes (from baseline) through Day 5	FAS	ANCOVA
3 Length of stay (# of days) in index ICU/CCU	FAS	Wilcoxon rank-sum test
4 Renal dysfunction or worsening of renal function through Day 5	FAS	chi-squared test
5 Time (days) to re-hospitalization due to HF and renal failure through Day 180	FAS	Kaplan-Meier estimates and log rank test
6 Time (days) to CV death or re-hospitalization due to HF/RF through Day 180	FAS	Kaplan-Meier estimates and log rank test
7 Time to in-hospital worsening heart failure through Day 5 defined by symptoms and signs		Kaplan-Meier estimates and log rank test
8 Use of loop diuretics and vasoactive agents through Day 5	FAS	chi-squared test
9 Changes in cardio-renal biomarkers (Day 2 and Day 5)	FAS	Summary statistics, see Section 2.2.3

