In addition, the Kaplan-Meier estimates of the survival functions for each treatment group will be plotted. The Kaplan-Meier estimates of the cumulative event rate will also be presented in tables by treatment group for each day and also by time interval.

For CV death, a patient without an event will be censored at the earlier of:

- Date of death for non-CV related causes
- The last date at which the vital status was known, including last visit or contact
- Day 180

An adjudicated death with unknown cause will be classified as a CV death. Similarly, investigator suspected deaths of unknown cause will be classified as CV deaths.

All-cause death through Day 180

All-cause death through Day 180 will be analyzed similarly to CV death through Day 180. A patient without an event will be censored at the last date at which the vital status was known (including last visit or contact) or at Day 180.

Of note, CV death and all-cause death will be two efficacy variables for bridging with other global studies.

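### CV death and all-cause death are tested and estimated without baseline covariates already collected at screening: a valid plan with a modest loss of efficiency

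*SAP*

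**What the plan says.** SAP 2.2.2 states that "CV death will be analyzed with a log-rank test" and that the hazard ratio with its 95% confidence interval is "estimated based on a Cox proportional hazards model with treatment assignment as a factor". It adds that "All-cause death through Day 180 will be analyzed similarly to CV death through Day 180". Protocol 9.5.1 agrees: "For CV death and all-cause death will be analyzed with a log-rank test". Neither text names a stratum or a covariate.

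Both endpoints are confirmatory: "The three secondary variables will be tested using hierarchical testing procedure in controlling overall" alpha, in the order WHF, CV death, all-cause death, once the primary endpoint is significant.

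The primary endpoint is handled differently. The protocol synopsis gives an "ordered logistic-regression (proportional odds) model that includes treatment and country as factors". SAP Table 2-5 lists the same kind of model with the second factor blacked out, and adds as a sensitivity analysis a "van Elteren extension of the Wilcoxon test stratified by" a factor that is also blacked out. So the SAP names a stratification factor where it intends to use one.

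Suitable baseline values exist. Protocol 4.1 makes age, systolic BP, BNP or NT-proBNP, and eGFR part of eligibility. SAP 2.1.6 summarises "Screening BNP, NT pro-BNP and estimated eGFR, laboratory values as reported by the investigator", and SAP 2.1.4 uses age, SBP and eGFR as subgroup variables. The only provision for adjustment is in protocol 9.2 and SAP 2.1.6: supplemental models may be run if an imbalance appears. The variables and the trigger are not named.

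**The concern.** The mortality endpoints get no adjustment, although covariates plausibly related to death are in hand for nearly every patient at no extra cost. In a survival model, leaving out a prognostic covariate costs some power. The documents state no power for mortality, and the trial is sized on the composite, so these endpoints have little to spare.

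There is also a pre-specification issue that does not depend on the size of the gain. Adjustment is left to a discretionary analysis triggered by an observed imbalance, and protocol 5.3 names no randomization strata that would limit imbalance by design. A covariate list fixed before unblinding removes that discretion.

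**Working it through.** **1. The plan's own figure.** Protocol 9.7 and SAP 2.7 give 1,520 patients for 80% power, two-sided 5%, common odds ratio 0.75. Protocol 6.4.3 gives placebo proportions of 11.9% failure and 26.0% success, so 62.1% no change. Applying odds ratio 0.75 gives 9.2 / 58.9 / 31.9% on serelaxin, and averages of 10.55 / 60.5 / 28.95%. Whitehead's formula for 1:1 allocation is

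N = 12(z₀.₉₇₅ + z₀.₈₀)² / [(ln 0.75)² (1 − Σp̄³)] = 12 × 7.849 / (0.08276 × 0.7531) ≈ 1,511.

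The stated 1,520 reproduces (power 80.2%). It concerns the composite only.

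**2. Mortality power without covariates.** Hazard ratio 0.63 is the 37% reduction reported for the earlier phase III trial (protocol 1.1). Schoenfeld: 4 × 7.849 / (ln 0.63)² = 31.40 / 0.2135 = 147.1, so 148 events for 80% power. The documents give no Day-180 rate, so the placebo rate r is assumed. With 760 per arm, events = 760r + 760[1 − (1 − r)^0.63], and power = Φ(0.462 × √events / 2 − 1.96):

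| Assumed placebo rate | Events | Power |
|---|---|---|
| 6% | 75 | 51% |
| 10% | 125 | 73% |
| 15% | 188 | 89% |

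**3. Effect of adjustment.** Simulation: 1,520 patients 1:1, eight countries, exponential survival censored at Day 180, hazard ratio 0.63 conditional on covariates, one-sided 0.025, 4,500 trials per row. The covariates are represented by one normal risk index. The log-hazard SDs of the index and of country are assumptions.

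| Placebo rate | SD index / country | Treatment only | Country-stratified | Index + country | Gain (points) |
|---|---|---|---|---|---|
| 10% | 0.5 / 0.2 | 70.2% | 70.1% | 70.9% | 0.7 |
| 10% | 0.8 / 0.3 | 68.4% | 68.5% | 71.6% | 3.2 |
| 10% | 1.0 / 0.4 | 66.4% | 66.5% | 71.8% | 5.4 |
| 6% | 0.8 / 0.3 | 49.3% | 49.2% | 50.8% | 1.5 |
| 15% | 0.8 / 0.3 | 84.0% | 84.2% | 87.4% | 3.4 |

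The Monte Carlo standard error of a single power figure is about √(0.684 × 0.316 / 4,500) = 0.7 points, so the smallest gains are close to noise. Country stratification alone moves power by 0.2 points or less, in either direction. With no index effect and country SD 0.4 it gives 70.8% to 71.0%.

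**4. Hazard ratio.** The treatment-only estimate averages 0.63 to 0.65 across these rows, against 0.62 to 0.63 with full adjustment.

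**5. Validity.** With a true hazard ratio of 1 (10% rate, SDs 1.0 / 0.4), one-sided type I error is 2.3% for treatment-only and 2.5% for the fully adjusted analysis.

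**The case against.** The strongest case for leaving the plan alone is that an unstratified log-rank test is valid in a randomized trial, that protocol 5.3 names no randomization strata it would ignore, and that covariate adjustment is partly a matter of preference. That stands, and it limits this to an efficiency point.

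Bridging also favours a simple estimate. SAP 2.2.2 says the two mortality endpoints are for bridging with other global studies, and the documents do not show that those studies use the same covariates. That stands too, and is why the unadjusted result must remain visible.

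The size of the gain is uncertain. Protocol 1.1 calls congestion status prognostic, and 6.4.4.4 refers to baseline biomarkers of risk, but no effect sizes are given. Eligibility also narrows three of the covariates: SBP 125 to 180 mmHg, eGFR 25 to 75, and BNP at least 500 or NT-proBNP at least 2,000 pg/mL. An SD near 1.0 is therefore on the optimistic side. The simulation also enters the true index, whereas a real model must estimate several coefficients.

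Three stronger readings are tempting, and the documents do not support them:

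- A reader might infer that leaving out country, which the primary model includes, is the main fault. The calculation shows that country alone recovers almost nothing. The documents give no mortality by country, and protocol 1.1 reports no marked differences among guidelines, only some variation in approved drugs.
- A reader might infer that the treatment-only hazard ratio is biased towards 1. The shift is small and reflects a marginal rather than a conditional estimand, because the hazard ratio is non-collapsible.
- A reader might infer that the subgroup analyses or the supplemental analyses already cover the point. The subgroups do not adjust the overall comparison, and the supplemental analyses are optional with no variables named.

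**Conclusion.** The point holds as a modest, inexpensive improvement. The plan names no strata and no covariates for two endpoints in the confirmatory sequence, while suitable baseline values are collected as part of eligibility. The planned analysis is not wrong. Adjustment would add about 1 to 5 points of power, nearly all of it from the prognostic covariates.

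This rests on assumptions the documents cannot confirm: placebo Day-180 rates of 6 to 15%, a hazard ratio of 0.63, a covariate log-hazard SD of 0.5 to 1.0, a country SD of 0.2 to 0.4, and eight countries. If the covariates are only weakly prognostic, the power gain is negligible and the remaining benefit is a covariate list fixed in advance.

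**What to change.** Before unblinding, amend SAP 2.2.2 and protocol 9.5.1 to name one Cox model for CV death and for all-cause death. It should contain treatment, age, screening SBP (stating which screening reading), eGFR and log natriuretic peptide, with country as a stratum or factor.

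- **One model for test and estimate.** Take both the confirmatory test of treatment and the adjusted hazard ratio with its confidence interval from this model, so that they agree. Stratifying the log-rank test by country and adding the covariates only to the hazard-ratio model would leave the test without the gain, and the two could disagree.
- **Peptide.** Eligibility accepts either BNP or NT-proBNP, measured locally. Standardise within assay, or use the baseline NT-proBNP biomarker of protocol 6.4.4.4 if it was drawn before the infusion.
- **Rules.** Fix a pooling rule for small countries and a simple rule for missing covariates.
- **Bridging.** Report the unadjusted log-rank test and the treatment-only hazard ratio alongside, not as an afterthought.

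The cost is wording in two documents and the two rules above; no new data are needed. The main downside is that the adjusted hazard ratio is conditional on the chosen covariates, so comparison with the global studies should use the unadjusted figure unless those studies adjust in the same way.
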